from the parent EOS Visit performed outside this allowed time window, assessments will need to be performed again at the Study CLIN-60120-452 Inclusion Visit (flagged with *). However, to enable continued access to the Investigational Product and rollover of participants with impaired mobility [in the case(s) when per investigator's judgement this is considered as beneficial for the participant's medical conditions], the parent EOS Visit and consenting for CLIN-60120-452 and CLIN-60120-452 Inclusion Visit can be conducted remotely. In such case(s) both parts of remote consenting used by the site – i.e. Informing/Consenting discussion and ICF signature should be agreed with the IRB/EC, and the investigator's judgement should be sufficiently documented in the patient source notes.

For the spinal health assessment, a time window of 3 months post parent visit is allowed (flagged with **).

- b. Follow-up Visits will be either in-clinic or performed remotely (e.g. at the participant's home by qualified SP in-home services, and/or via video-conference or telephone contact from clinical site personnel).
- c. The EOS/EW Visit will be ideally an in-clinic visit (or remotely when permitted by the IRB/IEC) and will occur at the time of last study intervention intake. The EOS Visit must take place before the participant transitions to commercial treatment.
- d. For participants <18 years, assent and legal guardian's consent will also be required.
- e. Palovarotene status (treated or not treated) and regimen (chronic or flare-up treatment) at the time of transition to Study CLIN-60120-452 will be collected at the Inclusion Visit. Participants will be supplied with chronic treatment as well as the appropriate dose of palovarotene to initiate flare-up treatment when a flare-up or traumatic event is confirmed by the investigator. Participants will be instructed to report potential flare-up symptoms to study site personnel, only one symptom is required to define a flare-up (see Section 6.1). In the presence of persistent flare-up symptoms, treatment may be extended in 4-week intervals until the flare-up symptoms resolve. If the participant experiences an intercurrent flare-up, or substantial high-risk traumatic event likely to lead to a flare-up, at any time during the flare-up treatment, the 12-week flare-up treatment should be restarted.

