4.3 Justification for Dose

The proposed dosing for palovarotene consists of 5 mg once daily (chronic treatment) with an increase in dose at the time of a flare-up to 20 mg once daily for 4 weeks (28 days), followed by 10 mg once daily for 8 weeks (56 days) for a total of 12 weeks (84 days) (20/10 mg flare-up treatment) even if symptoms resolve earlier. In the presence of persistent flare-up symptoms, treatment may be extended in 4-week intervals with 10 mg palovarotene and continued until

the flare-up symptoms resolve. Should the participant experience an intercurrent flare-up (new flare-up location or marked worsening of the original flare-up) at any time during flare-up treatment, the flare-up 12-week treatment should be restarted (see Section 6.1). In the case of adverse reactions, the daily dose can be reduced (see Section 6.5). If dose reduction does not alleviate the adverse reactions, then the participant may take palovarotene only at the time of a flare-up (or substantial high-risk traumatic event) (Section see 6.1).

Participants are eligible for the study whether they are receiving chronic or flare-up treatment in the parent study at the time of transition. Participants who previously interrupted/stopped palovarotene treatment and are currently under parent study follow-up are also eligible if they meet eligibility criteria. As this is a rollover study with the aim of providing treatment continuity, the dose of palovarotene administered will be individualised for each participant and based on the regimen (chronic or flare-up treatment) and dose they received during their participation in the parent study at the time of transition to Study CLIN-60120-452 or prior to interrupting/stopping palovarotene treatment (to allow for dose modifications made to the standard chronic/flare-up during the parent study).

The proposed chronic/flare-up regimen was selected based on nonclinical and clinical data.

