6.1 Study Intervention Administered

The study intervention administered is palovarotene. Participants are eligible for the study whether they are receiving chronic or flare-up treatment in the parent study at the time of transition. Participants who previously interrupted/stopped palovarotene treatment and are currently under parent study follow-up are also eligible if they meet eligibility criteria. As this is a rollover study with the aim of providing treatment continuity, the dose of palovarotene administered will be individualised for each participant and based on the regimen (chronic or flare-up treatment) and the dose they received during their participation in the parent study at the time of transition to Study CLIN-60120-452 or prior to interrupting/stopping palovarotene treatment (to allow for dose modifications made to the standard chronic/flare-up regimen during the parent study).

In the completed parent studies PVO-1A-202/PVO-1A-204 and PVO-1A-301, participants received the chronic/flare-up regimen detailed in [Table 4](#) below (or the weight-based equivalent for <90% skeletally immature participants), with flare-up treatment extension in 4-week increments for persistent symptoms. In Study PVO-1A-301, anytime during flare-up treatment, the 12-week treatment restarts if the participant has another flare-up or a substantial high-risk traumatic event. In both parent studies, the daily dose of palovarotene can be reduced if the participant experiences AEs that are not tolerated.

Participants receiving flare-up treatment at the time of transition to Study CLIN-60120-452 will continue and complete the flare-up treatment as was planned in the parent study. Chronic daily treatment should then be re-initiated at 5 mg, or the dose received during participation in the parent study prior to the flare-up.

Treatment initiation (at the Inclusion Visit) for Study CLIN-60120-452 should ideally concur with the EOS Visit and the study intervention administration schedule of the parent study in order to ensure palovarotene treatment continuity for both chronic and flare-up treatment.

Details of the study intervention are provided in [Table 4](#).

Table 4 Study Intervention Administered

Intervention Name	Palovarotene
Intervention Description	Palovarotene hard capsules, taken once daily as chronic/flare-up treatment
Type	Drug
Dose Formulation	Capsule

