Unit Dose Strength(s)	Each capsule contains 1 mg, 1.5 mg, 2.5 mg, 5 mg or 10 mg of palovarotene as active ingredient
Dosage Level(s)	
Chronic/flare-up regimen:
 
Chronic treatment 5 mg once daily (or at the dose received during participation in the parent study at the time of transition to Study CLIN-60120-452, or prior to interrupting/stopping palovarotene treatment)
 
Flare-up treatment 20 mg once daily for 4 weeks (28 days) 10 mg once daily for 8 weeks (56 days) Persistent flare-up symptoms: extension of 10 mg once daily in 4-week increments Intercurrent flare-ups (new flare-up location or marked worsening of original flare-up): 12-week flare-up treatment should be restarted
 
Chronic treatment: once daily, 5 mg or at the dose received during participation in the parent study at the time of transition to Study CLIN-60120-452 or prior to interrupting/stopping palovarotene treatment.
 
Flare-up treatment: increase in dose at the time of a flare-up (or substantial high risk traumatic event likely to lead to a flare-up) to 20 mg once daily for 4 weeks (28 days), followed by 10 mg once daily for 8 weeks (56 days) for a total of 12 weeks (84 days) (20/10 mg flare-up treatment) even if symptoms resolve earlier.
 
Flare-up treatment should begin at the onset of the first symptom indicative of a FOP flare-up or substantial high-risk traumatic event likely to lead to a flare-up. Symptoms of a FOP flare-up typically include but are not limited to localised pain, soft tissue swelling/inflammation, redness, warmth, decreased joint range of motion, and stiffness. Chronic treatment should cease at the time of initiation of flare-up treatment, re-initiation of the chronic daily treatment should occur after completion of the flare-up treatment.
 
Flare-ups can occur in the absence of any apparent causative factor, but there is a high risk that substantial traumatic events (e.g. surgery, intramuscular immunisation, mandibular blocks for dental work, muscle fatigue, blunt muscle trauma from bumps, bruises, falls or influenza-like viral illnesses), can lead to a flare-up and result in heterotopic bone formation. Flare-up treatment should be initiated at the time of such events.
 
Persistent flare-up symptoms: treatment may be extended in 4-week intervals with 10 mg palovarotene and continued until the flare-up symptoms resolve.
 
Intercurrent flare-up: if the participant experiences an intercurrent flare-up (new flare-up location or marked worsening of the original flare-up) at any time during the flare-up treatment, then the 12-week flare-up treatment should be restarted.
 
In the case of any intolerable adverse reactions, the daily dose of the chronic/flare-up regimen can be reduced (see Section 6.5).
 
Flare-up only regimen: If the participant experiences intolerable adverse reactions while taking chronic daily treatment and dose reduction does not alleviate the adverse reactions, then the participant may take palovarotene only at the time of flare-up (or substantial high-risk traumatic event).

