Route of Administration	Oral
Use	Active study intervention
IMP and NIMP/AMP.	IMP
Sourcing	Centrally by sponsor

Packaging and Labelling	
Study intervention will be provided in bottle or blister packaging:
 
 - 90 capsules packaged in a bottle (1 mg, 1.5 mg, 2.5 mg, 5 mg and 10 mg). - 14 capsules packaged in a blister (1 mg, 1.5 mg and 5 mg) - 15 capsules packaged in a bottle (5 mg) for US patients only. 
Each carton will be labelled as required per country requirement.

Storage requirements	To be stored at room temperature (between 15°C and 30°C) and protected from light and humidity.
Former Names/Alias(es)	None

AMP=auxiliary medicinal product; FOP= fibrodysplasia ossificans progressiva; IMP=investigational medicinal product; NIMP=non investigational medicinal product.

Participants will be instructed to report potential flare-up symptoms to study site personnel. Only one symptom is required to define a flare-up. If these symptoms are consistent with previous flare-ups, include a participant-reported onset date, and are confirmed by the investigator as associated with a flare-up, participants will immediately begin flare-up-based treatment. Flare-up based treatment should also be initiated if the investigator confirms the presence of a substantial high-risk traumatic event likely to lead to a flare-up.

Based on clinical signs and symptoms as determined by the investigator, flare-up treatment may be extended in 4-week intervals while on-treatment with 10 mg palovarotene and continue until the flare-up resolves and the 4-week extension treatment has been completed.

Participants will be supplied with chronic treatment as well as the appropriate dose of palovarotene to initiate flare-up treatment when a flare-up or traumatic event is confirmed by the investigator (during in-clinic or remote visit, or by telephone contact).

Participants will be instructed to contact study site personnel immediately in case of intolerable adverse reactions during palovarotene treatment. The investigator will assess the adverse reaction and, if appropriate, will instruct the participant to reduce the daily dose of palovarotene as described in Section 6.5. If the participant does not have the appropriate dose in his/her possession, the study site will make immediate arrangements to ship the appropriate palovarotene dose to the participant.

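### The protocol's passages on restarting the 12-week flare-up course name different triggers, leaving open what happens after a traumatic event during a running course

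*Protocol*

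**What the plan says.** **Restart.** Protocol Table 1, footnote e, gives two triggers for restarting the 12-week course: "If the participant experiences an intercurrent flare-up, or substantial high-risk traumatic event likely to lead to a flare-up". SAP 2.5, footnote e, repeats this. Table 4 gives one trigger, stated twice: "Intercurrent flare-ups (new flare-up location or marked worsening of original flare-up): 12-week flare-up treatment should be restarted", and again "if the participant experiences an intercurrent flare-up (new flare-up location or marked worsening of the original flare-up) at any time during the flare-up treatment". The synopsis carries the same rule, Section 4.3 matches it ("Should the participant experience an intercurrent flare-up (new flare-up location or marked worsening of the original flare-up"), and so does SAP 2.2. SAP 5.7.3.7 also defines an intercurrent flare-up without mentioning trauma.

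**Traumatic events.** After listing examples of such events, Table 4 says: "Flare-up treatment should be initiated at the time of such events". The synopsis, Section 4.3 and the text after Table 4 say much the same, subject to confirmation by the investigator. Section 6.1 also states the wider restart rule, "the 12-week treatment restarts if the participant has another flare-up or a substantial high-risk traumatic event", but as the rule of parent Study PVO-1A-301.

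**Extension for persistent symptoms.** Table 4 says "treatment may be extended in 4-week intervals with 10 mg palovarotene and continued until the flare-up symptoms resolve". The synopsis, footnote e and Section 4.3 also end the extension at symptom resolution. The text after Table 4, in the same Section 6.1, says treatment should "continue until the flare-up resolves and the 4-week extension treatment has been completed".

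**The concern.** The restart sentences do not list the same triggers. A site working from the Schedule of Activities would return a participant to 20 mg after a confirmed traumatic event in mid-course. A site working from the restart line of Table 4 could leave the participant on the running schedule. The protocol treats a traumatic event as something that may lead to a flare-up, not as a flare-up, so the two triggers cannot be taken as synonyms.

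The listed events include falls, intramuscular immunisation, muscle fatigue and influenza-like illness. Participants who transfer in mid-course also finish it as planned in the parent study, which for PVO-1A-301 brings in the wider rule.

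What is at stake is exposure to the higher doses in a study whose primary objective is safety. Section 2.2.3 reports that mucocutaneous events leading to dose reduction were more common on 20/10 mg than on chronic treatment, and Table 2 describes mucocutaneous toxicity of systemic retinoids as dose-dependent.

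**Working it through.** **Inputs.** The synopsis and Table 4 give 28 days at 20 mg, then 56 days at 10 mg, 84 days in all, and a chronic dose of 5 mg or the parent-study dose. I assume 5 mg, no dose reduction and no extension in progress.

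**The plan's own figure.** 28 + 56 = 84 days, as stated. One course is 28 × 20 + 56 × 10 = 1120 mg.

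**Restart.** Suppose a traumatic event is confirmed after d days of a course (d from 1 to 84) and no intercurrent flare-up follows. Compare both readings over the same d + 84 days.

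- No restart: 84 days on flare-up doses, then d days at 5 mg. Total 1120 + 5d mg.
- Restart: d days of the first course, then a full second course. Total C(d) + 1120 mg, where C(d) = 20d for d ≤ 28 and 560 + 10(d − 28) for larger d.
- Difference: d more days on flare-up doses, and C(d) − 5d mg.

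| d | Flare-up-dose days, no restart / restart | Days at 20 mg, no restart / restart | Total mg, no restart / restart | Net mg |
|---|---|---|---|---|
| 1 | 84 / 85 | 28 / 29 | 1125 / 1140 | 15 |
| 14 | 84 / 98 | 28 / 42 | 1190 / 1400 | 210 |
| 28 | 84 / 112 | 28 / 56 | 1260 / 1680 | 420 |
| 56 | 84 / 140 | 28 / 56 | 1400 / 1960 | 560 |
| 84 | 84 / 168 | 28 / 56 | 1540 / 2240 | 700 |

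**Extension.** Earlier blocks run in full under either wording because symptoms persist. Only the last block of an episode can differ. If symptoms resolve on day r of that block, completing it adds 28 − r days at 10 mg, and (10 − 5) × (28 − r) mg over chronic dosing. For r = 1 this is 27 days and 135 mg; for r = 28 it is zero.

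**Derived variables.** I checked whether the ambiguity carries into the analysis.

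- Dose at AE onset is the latest dosing-log record before the event (SAP 5.7.2.2).
- Exposure periods are built from recorded start dates, and flare-up duration from recorded cycle dates (SAP 5.8.2 and 5.8.2.2).
- Expected dose for compliance uses the first and last dose dates of each cycle (SAP 5.6), so a longer course raises both numerator and denominator.

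**The case against.** No passage says that the course restarts solely for an intercurrent flare-up. The trauma statements stand close to the restart sentences and exempt nobody who is already on treatment. Starting the 20/10 mg course during a running one is in effect a restart, so footnote e may only combine two adjacent rules, in line with PVO-1A-301. This has force: the text is better called ambiguous than flatly contradictory. It does not remove the point. The trauma statements speak of starting treatment, the rule written for events during a course leaves trauma out, and only footnote e applies the wider trigger to this study.

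The case is also narrow. One symptom suffices to define a flare-up. If the trauma leads to a flare-up at a new site, or to marked worsening, every passage restarts the course and the readings differ only in timing. That stands and limits the point.

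On extensions, treatment given in 4-week intervals is naturally read as whole blocks, and the text after Table 4 then only makes that explicit. That also stands: the wordings conflict only if stopping within a block is allowed.

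Finally, the analysis outputs are descriptive and follow recorded dosing, so they would still show what participants received. That stands in full.

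**Conclusion.** The restart passages need reconciling. For a confirmed traumatic event during a course, with no intercurrent flare-up afterwards, the reading chosen changes exposure by 1 to 84 flare-up-dose days, up to 28 of them at 20 mg, and by up to 700 mg net. These are per-event figures resting on the assumptions above; the milligram figures change with another chronic dose. The extension wording is a lesser matter: 0 to 27 days at 10 mg, once per episode, and only on the mid-block reading.

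Three stronger conclusions might be inferred, and the documents support none of them.

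- That exposure, dose-at-onset or compliance results would be wrong. They follow what was recorded. The inconsistency lies in what participants are given at different sites.
- That a late restart costs the full 1120 mg. The participant would otherwise have taken 84 × 5 = 420 mg over the same days, which leaves 700 mg.
- That the study-level safety results shift by a known amount. The frequency of such events during a course is not given.

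**What to change.** Reconcile footnote e of Table 1, the synopsis, Section 4.3, Table 4 and the text after Table 4 in the protocol, and Sections 2.2 and 2.5 of the SAP, so that all state one restart rule and one extension end rule. The restart rule should say expressly what happens when a traumatic event is confirmed during a running course. The extension rule should say whether a block that has begun is completed. Which rules apply is a clinical decision for the sponsor.

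The cost is a protocol clarification and matching SAP text; no analysis method changes. Recording the reason for each restart would help interpretation, but this is secondary: the case report form is not available here, and Section 8.1.7 already collects flare-up cause and location.

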2 INTRODUCTION

Palovarotene is an orally bioavailable retinoic acid receptor gamma (RAR γ) selective agonist that is being developed by Ipsen for the prevention of heterotopic ossification (HO) in adults and children with fibrodysplasia (myositis) ossificans progressiva (FOP).

2.1 Study Rationale

Currently there are no commercially available effective treatments to prevent the formation of heterotopic bone in FOP. Therapeutic approaches are limited to symptom management and flare-up prevention ([Kaplan et al., 2019a](#); [Meyers et al., 2019](#)).

The clinical safety and efficacy of palovarotene in reducing new HO in FOP has been evaluated and demonstrated in:

- Study PVO-1A-201 (complete), a phase II, randomised, double-blind, placebo-controlled study;
- Study PVO-1A-202 (Part A and B complete, Part C and D complete; Parts B, C and D correspond to Study PVO-1A-204 in France), an open-label extension of Study PVO-1A-201;
- Study PVO-1A-301 (Part A, B and C complete), a phase III, single-arm, open-label study.

The aim of this study is to provide continued access to an effective treatment for FOP for which there is no alternative once the ongoing clinical studies have ended. More specifically, the aim is to provide treatment continuity to participants who have completed one of the parent studies (Study PVO-1A-301 or PVO-1A-202/PVO-1A-204) and, in the investigator's judgement, may benefit from palovarotene therapy until palovarotene is reimbursed in the country where the study is being conducted, or another access programme becomes available, or until the study end date of November 2024 is reached, whichever occurs first.

2.2 Background

2.2.1 Disease Background

Fibrodysplasia ossificans progressiva (Online Mendelian Inheritance in Man (OMIM) #135100) is an ultra-rare genetic disorder, with an estimated prevalence of 1.36 per million individuals ([Baujat et al., 2017](#)).

FOP is caused by a spontaneous missense mutation in the activin A receptor type-1 (*ACVR1*)/activin receptor-like-kinase-2 (*ALK2*) gene, which encodes a receptor in the bone morphogenetic protein (BMP) signalling pathway ([Pignolo et al., 2013](#); [Zhang et al., 2013](#)). Bone morphogenetic proteins are extracellular ligands belonging to the transforming growth factor beta (TGF- β) superfamily. Signal transduction studies show that receptor-regulated Smad proteins 1/5/8 are the immediate downstream molecules of BMP receptors and play a central role in BMP signal transduction ([Sanchez-Duffhues et al., 2016](#); [Shen et al., 2009](#)).

Following ligand binding to BMP receptors, there is downstream activation of genes involved in the differentiation and activation of osteoblast and chondrocyte-like cells via phosphorylation of Smad proteins 1/5/8; this is regulated by the inhibitory factor 12-kDa FK506-binding protein (FKBP12), which binds to the BMP type 1 receptor and stabilises the inactive form ([Sanchez-Duffhues et al., 2016](#); [Shen et al., 2009](#)). In the presence of the mutated *ACVR1/ALK2* gene, FKBP12 binding is reduced, leading to enhanced BMP signalling ([Sanchez-Duffhues et al., 2016](#)).

Patients with FOP experience sporadic and unpredictable episodes of soft-tissue swelling, pain, reduced movement, stiffness and fever, referred to as 'flare-ups' ([Di Rocco et al., 2017](#); [Kaplan et al., 2019a](#); [Pignolo et al., 2013](#); [Pignolo et al., 2016](#)). Flare-ups appear spontaneously

or after muscle fatigue, minor trauma, intramuscular injections or influenza-like viral illnesses, and develop rapidly over several hours ([Kaplan et al., 2019a](#)); these inciting events induce local inflammation, which is followed by recruitment of bone progenitor cells that differentiate into chondrocytes ([Shimono et al., 2011](#)). Although some flare-ups regress spontaneously, many appear to lead to HO, which transforms soft and connective tissues (including aponeuroses, fascia, ligaments, tendons and skeletal muscles) into heterotopic bone ([Kaplan et al., 2019a](#); [Pignolo et al., 2013](#)). Of patients with FOP, 95% manifest HO before reaching 15 years of age ([Qi et al., 2017](#)).

FOP is characterised by congenital malformation of the great toes and progressive HO in soft and connective tissues; it is a severely disabling HO disorder ([Baujat et al., 2017](#); [Pignolo et al., 2016](#)). Other clinical features observed in patients with FOP are shortened thumbs, cervical spine malformations, short broad femoral necks and proximal medial tibial osteochondromas ([Kaplan et al., 2009](#); [Pignolo et al., 2013](#)). Typically, HO begins in the dorsal, proximal, axial and cranial regions of the body (neck, shoulders and back) and progresses into ventral, caudal and distal regions (trunk and limbs) ([Hüning and Gillessen-Kaesbach, 2014](#)). Heterotopic ossifications develop into ribbons, sheets and plates of extra bone throughout the body and across joints, thereby progressively restricting movement ([Baujat et al., 2017](#)). Once ossification occurs, it is permanent; consequently, disability in FOP is cumulative, with most patients becoming immobilised and confined to a wheelchair by their third decade of life and requiring lifelong assistance in performing activities of daily living (ADL) ([Baujat et al., 2017](#); [Mattera et al., 2015](#); [Ortiz-Agapito and Colmenares-Bonilla, 2015](#); [Pignolo et al., 2013](#); [Pignolo et al., 2020a](#)).

FOP is not only an extremely disabling disease but also a condition of considerably shortened lifespan ([Kaplan et al., 2010](#)). Morbidity associated with FOP includes fractures (due to the increased risk of falls, immobility and prednisone use), limb swelling, pressure sores, hearing impairment, gastrointestinal issues and pain ([Kaplan et al., 2019b](#); [Peng et al., 2019](#)). Patients with FOP reach a median survival of 56 (95% confidence interval (CI): 51; 60) years; death is often due to cardiorespiratory failure (as a result of respiratory insufficiency, which is usually caused by progressive restrictive chest-wall HO) or thrombosis ([Baujat et al., 2017](#); [Di Rocco et al., 2017](#); [Kaplan et al., 2010](#); [Pignolo et al., 2013](#)).

There are currently no effective treatments to prevent the formation of heterotopic bone in FOP, with therapeutic approaches being limited to symptom management and flare-up prevention; consequently, there is a critical unmet need for definitive therapies for patients with FOP ([Kaplan et al., 2019a](#); [Meyers et al., 2019](#)).

